8.4. Accountability of Investigational Drug Supplies

The active drug and placebo will be prepared by the University of Rochester Medical Center Investigational Drug Service, which will also administer the drug to study participants during their hospital admission. Remaining doses of the drug will be given to each subject at the time of hospital discharge. From that point forward, the subject will be responsible for storing and administering the drug as an outpatient.

8.5. Discontinuation of Study Drug by Subject

Subjects will be free to stop the study drug at any time. Should they do so, they will be withdrawn from the study.

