3. CHARACTERISTICS OF THE RESEARCH POPULATION

3.1. Subject Characteristics

- a) **Number of Subjects:** The planned enrollment is 40 patients over 12 months in order to achieve a final sample size of 30 subjects, assuming a dropout rate of 25% during the course of the study. This projected sample size and time frame represent a conservative estimate based on the 56 acute ischemic stroke patients who were admitted to Strong Memorial Hospital with an isolated visual field deficit between January 1, 2015 and December 31, 2015. This sample size is comparable to equivalent pilot trials evaluating the efficacy of an approved drug for a novel indication. If any subjects withdraw from the study, they will be replaced to meet this enrollment goal.
- b) **Gender and Age of Subjects:** Men and women between 18 and 85 years of age will be enrolled in the study. Patients older than 85 will be excluded because advanced age is associated with increased risk of adverse side effects from SSRIs. Furthermore, the ability to fixate and produce reliable visual field measurements deteriorates with increasing age.
- c) **Racial and Ethnic Origin:** Subjects of all racial and ethnic backgrounds will be enrolled in the study.
- d) **Vulnerable Subjects:** Subjects who are vulnerable to coercion or undue influence will not be enrolled, including children, pregnant women, students, employees, prisoners, and persons with decisional impairments.

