3. Automated Humphrey perimetry: Humphrey perimetry is an automated non-invasive clinical test performed in most routine ophthalmologic evaluations to characterize and monitor a patient's peripheral vision, using normative data from healthy age-matched controls as a reference. In this study, we will use Swedish Interactive Threshold Algorithm (SITA) standard 24-2 visual field testing to assess each subject's peripheral vision at the specified time points. This form of automated Humphrey perimetry requires 7 ½ minutes of testing time. Testing will be performed by a qualified ophthalmic technician or physician at the University of Rochester Flaum Eye Institute. During each test, the subject will place his or her chin on a chin rest, fixate on a central point, and respond with a push-button when he or she sees a test spot presented briefly in the peripheral visual field. Baseline, 90-day, and 6-month assessments represent standard care, whereas the 30-day assessment is for research purposes only.
4. Optical coherence tomography (OCT): This is a standardized non-invasive clinical test that uses light waves to measure the thickness of the RNFL in patients with a wide range of visual problems. It requires 30 seconds of testing time. It will be performed by a qualified ophthalmic technician or physician at the University of Rochester Flaum Eye Institute. OCT is not part of standard care for this patient population.
5. Patient Health Questionnaire-9 (PHQ-9): This is a self-report inventory used as a screening and diagnostic tool for depression (Appendix F). The 9 items are based on

the 9 diagnostic criteria for depression included in the Diagnostic and Statistical Manual of Mental Disorders IV. It takes 5-10 minutes to complete. It will be administered at baseline, 30 days, 90 days, and 6 months. The 30- and 90-day assessments will be performed during routine follow-up in the University of Rochester Stroke and Cerebrovascular Disorders Clinic. The 6-month assessment will be performed by phone interview. Screening for depression by PHQ-2, a shorter version of PHQ-9, is part of standard care for this patient population at baseline. However, screening by PHQ-9 is not part of standard care at baseline or at any other study time point.

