7. SUBJECT WITHDRAWALS

Subjects will be advised on the written informed consent form (Appendix A) that they have the right to withdraw from the study at any time without prejudice. Subjects may also be withdrawn from the study by study investigators if they have a recurrent stroke, a symptomatic hemorrhagic transformation of the index ischemic stroke, or another major illness requiring hospitalization, if they become pregnant, or if they are not able to comply with the study protocol or return for routine and study-specific neurological or ophthalmological assessments. Subjects withdrawn from the study will be replaced.

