8.6. Emergency Drug Disclosure

The University of Rochester Medical Center Investigational Drug Service will maintain a list of treatment assignments for each subject and disclose this information upon request in case of a medical emergency. Should drug disclosure occur, the subject in question will be withdrawn from the study.

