13. DATA ANALYSIS AND MONITORING

13.1. Sample Size Determination

The currently planned enrollment target of 40 subjects (*i.e.* 20 subjects per arm) is intended to achieve a final sample size of 30 and assumes a dropout rate of 25% during the course of the study. In turn, this estimate is based on the number of acute ischemic stroke patients who presented to Strong Memorial Hospital with an isolated visual field deficit in the previous calendar year (56 patients between January 1, 2015 and December 31, 2015). Previous studies indicate that 50% of patients will experience an improvement in their visual field deficit by 3 months. Based on this rate of spontaneous recovery, a final sample size of 15 subjects per group will provide 80% power to detect an improvement rate of 90% in the actively treated group (*i.e.* a 40% difference between the fluoxetine and placebo groups), using a one-sided χ^2 test with $\alpha = 0.05$. Thus, the planned sample size will be sufficient to detect a moderately large effect and is comparable to sample sizes used in equivalent pilot trials evaluating the efficacy of an FDA-approved drug for a novel application.

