13.2. Planned Statistical Analysis

The primary endpoint will be an improvement in peripheral vision of at least 15 degrees in the affected visual field as measured by automated Humphrey perimetry at 6 months. The primary outcome will be compared between the treatment groups using an upper-tailed two-sample *t* test with $\alpha = 0.05$. Secondary outcome measures will include degree of cortical reorganization as assessed by fMRI, RNFL thickness as assessed by OCT, the functional vision score as assessed by the Guide for the Evaluation of Visual Impairment,

performance on neuropsychological testing, and scores on the mRS, PHQ-9, and VFQ-25.

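### Stopping study drug or emergency unblinding takes the subject out of the study before the 6-month endpoint, and no analysis set is named, which points to a completer comparison that can be biased

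*Combined protocol and SAP*

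**What the plan says.** - **Stopping drug (8.5):** "Subjects will be free to stop the study drug at any time. Should they do so, they will be withdrawn from the study".
- **Emergency unblinding (8.6):** "Should drug disclosure occur, the subject in question will be withdrawn from the study".
- **Other withdrawals (7):** "Subjects may also be withdrawn from the study by study investigators if they have a recurrent stroke". The section goes on to symptomatic hemorrhagic transformation, major illness, pregnancy and inability to comply or attend. These are discretionary, whereas 8.5 and 8.6 are not.
- **Replacement (7 and 3.1):** "Subjects withdrawn from the study will be replaced" and "If any subjects withdraw from the study, they will be replaced to meet this enrollment goal".
- **Sample size (13.1):** the 40 enrolled are "intended to achieve a final sample size of 30 and assumes a dropout rate of 25% during the course of the study". Power is computed on 15 per group.
- **Primary endpoint (13.2):** a gain of at least 15 degrees "in the affected visual field as measured by automated Humphrey perimetry at 6 months". Treatment lasts 90 days, so a subject who stops early leaves about three months or more before the endpoint.
- **Perimetry (5.2, item 3):** "Baseline, 90-day, and 6-month assessments represent standard care, whereas the 30-day assessment is for research purposes only".

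Section 13.2 gives the endpoint, a one-sided two-sample t test and the list of secondary outcomes. It gives no analysis set, no rule for missing outcomes and no sensitivity analysis. No section that can be read describes follow-up after withdrawal.

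**The concern.** Sections 8.5 and 8.6 end study participation, not only treatment. Add replacement, power resting on 30 of 40, and silence on the analysis set, and little is left to analyze except subjects who stayed. Randomization protects the comparison of everyone randomized. It does not protect a comparison of those who remained if the reasons for leaving relate to both arm and recovery. A real benefit could then be hidden, or a false one created. Replacement restores the count but not the randomized comparison.

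The documents describe one route by which loss could differ by arm. Depressed subjects are referred for treatment (10.1), other SSRIs are not allowed (6), and needing a listed drug may mean withdrawal (Appendix C). The motor-recovery trial cited in 1.2 saw less depression on fluoxetine, and 10.2 links depression to poor recovery. This route would remove poor recoverers mainly from placebo, which flatters placebo and costs power. Fluoxetine side effects (10.1) could act in either direction.

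Outcomes not collected after withdrawal cannot be recovered later. Without a stated set, the choice would be made with data in hand, and 8.3 leaves the statistician unblinded.

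**Working it through.** **1. The plan's own figures.** From 13.1: 50% vs 90%, 15 per group, one-sided chi-square, alpha 0.05.
- Enrollment: 30 / 0.75 = 40, as stated.
- Power by the normal approximation: [0.4·√15 − 1.645·√(2·0.7·0.3)] / √(0.25 + 0.09) = (1.549 − 1.066) / 0.583 = 0.83, which gives 79.6%. The stated 80% reproduces.
- By exact binomial enumeration, the uncorrected chi-square has 83.4% power and 5.0% type I error. The t test of 13.2 on a 0/1 outcome has 79.3% and 4.9%.

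The 80% is therefore a figure for completers.

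**2. Assumptions for the illustration.** The 50% placebo rate is what 13.1 gives for 3 months; it is used here for 6 months. There are 15 completers per arm. Forced withdrawals are either 5 or all 25 of the 25 percentage points of loss, because the documents do not give the share. All other loss is random. Non-improvers are k = 2 or 3 times as likely to leave, in one arm only.

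**3. Improvement rate among those who remain.** With true rate p and forced loss f, improvers leave with probability x = f / [p + (1 − p)k], and the remaining rate is p(1 − x) / (1 − f). Further random loss does not change it. With p = 0.5:
- f = 0.05: k = 2 gives x = 0.0333 and rate 0.509; k = 3 gives x = 0.025 and rate 0.513.
- f = 0.25: k = 2 gives x = 0.1667 and rate 0.556; k = 3 gives x = 0.125 and rate 0.583.

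**4. Effect on the test (exact enumeration, 15 per arm).**

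| Forced loss | k | Selection on placebo only: power vs 90%, chi-square | Same, t test | Selection on fluoxetine only, no effect: type I error, chi-square |
|---|---|---|---|---|
| random | 1 | 83% | 79% | 5.0% |
| 5 points | 2 | 82% | 78% | 5.6% |
| 5 points | 3 | 81% | 77% | 5.8% |
| 25 points | 2 | 75% | 69% | 9.1% |
| 25 points | 3 | 69% | 64% | 11.8% |

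With the t test, type I error hardly changes (11.6% in place of 11.8% in the last row). If both arms lose 25% with equal selectivity (k = 2 or 3), type I error is 5.1%. With k = 3 on fluoxetine and k = 2 on placebo it is 6.9%.

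**5. Does a simple missing-data rule solve it?** Count missing as not improved, with no drug effect, 20 per arm, and purely random loss of 15% on fluoxetine and 35% on placebo. The rates become 0.5·0.85 = 0.425 and 0.5·0.65 = 0.325, and the one-sided chi-square rejects in 15.4% of trials (1.0% with the losses reversed).

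**6. Does imputation solve it?** This was simulated with 20 per arm, 25% missing, 85% assumed agreement between 90-day and 6-month status, and fluoxetine non-improvers at 90 days lost 3 times as often. With 90-day status known for all, type I error falls from 9.6% (completers) to 5.5%. If loss follows the 6-month result itself, it falls from 11.9% to 8.2%. If 90-day status is missing as well, there is no reduction: about 10% stays about 10% and about 12% stays about 12%, with power about 81%.

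**The case against.** Several points on the other side stand.

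- **Exclusion is inferred.** A reader might conclude that the plan drops withdrawn subjects from the analysis. No sentence says so. The consent form (Appendix A) and the authorization to release medical information (Appendix I) cannot be read here and might allow later perimetry to be used. Neither would supply an analysis set.
- **The depression route is weak and points one way.** Premorbid depression and current antidepressants are exclusions (3.2). Referral need not lead to a listed drug, and Appendix C says only that withdrawal may be needed. Section 1.2 holds that motivation probably matters less for vision. What the route threatens is power. A reader might infer that the plan inflates false positives, but that requires non-improvers to leave fluoxetine selectively, and the documents give no more than the possibility of side effects.
- **Extreme figures are bounds.** If every forced withdrawal in one arm is a non-improver and all 25% loss is forced, type I error reaches 23.9% or power drops to 51%. Nothing in the documents supports either as an expectation.
- **The effect may be small.** If these rules cause 5 points of the loss, the cost at 2–3 times is under one point of type I error and about 1–2 points of power.
- **The setting is modest.** The protocol compares itself with pilot trials and lists feasibility as an objective. Replacement could also leave more than 15 completers per arm.

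These limit the size of the concern but do not remove it. The rules as written stop outcome collection, and the plan offers no way to tell the harmless case from the harmful one.

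**Conclusion.** The concern holds as a design weakness of unknown direction and size. Mandatory withdrawal from the study under 8.5 and 8.6, replacement, and the absence of an analysis set in 13.2 lead by inference to a completer comparison. It is biased only if loss relates to both arm and recovery. In the direction of the documents' own route the harm is lost power, and in the opposite direction it is a raised type I error. The sizes in the table rest on the assumed forced share, the 2–3 fold selectivity in one arm, a 3-month rate used at 6 months, and 15 completers per arm. The documents do not support saying that the result will be biased, or which way. The change is still worth making before enrollment, because uncollected outcomes are lost for good and the remedy is inexpensive.

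**What to change.** 1. **Sections 7, 8.5 and 8.6.** Leave unchanged when drug is stopped and when the blind is broken. State that stopping study drug, or unblinding, is not leaving the study. Obtain the standard-care 90-day and 6-month perimetry for every randomized subject who has not withdrawn consent to follow-up, and check that Appendices A and I allow this.
2. **Section 13.2, analysis set.** Make the primary analysis all randomized subjects as assigned, using all available 6-month perimetry, including after drug was stopped. Keep replaced subjects in the analysis, and say whether the 40 includes replacements. Report withdrawals by arm and reason.
3. **Section 13.2, missing data.** Pre-specify one method with sensitivity analyses. Multiple imputation by arm from earlier perimetry is one option, with a small model given about 20 per arm; it reduces bias only where 90-day perimetry was obtained. Counting missing as not improved should not be the sole primary rule, for the reason in step 5.

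**Cost.** A wording amendment, some extra follow-up and analysis work, and possible dilution. With 20 per arm, all followed, and 50% vs 90%, power is 91% (exact, one-sided chi-square). If a quarter of the fluoxetine arm stop and improve at 70%, the arm's rate is 0.75·0.9 + 0.25·0.7 = 0.85 and power is 79%. If they improve at 50%, the rate is 0.80 and power is 65%. Section 13.1 should state these figures.

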5.3. Safety Assessments

Subjects will be instructed to exercise caution when drinking alcohol or taking any previously prescribed sedating medications, such as diphenhydramine or cyclobenzaprine, while on the study drug. Additionally, they will be advised to contact their primary care physicians or the study team before starting any new prescription or over-the-counter medications, or any new herbal or nutritional supplements. Primary care physicians will be provided with a list of medications and supplements to avoid while their patients are on the study drug.

Laboratory studies: A CBC and CMP will be repeated 30 days after the initiation of the study drug to monitor for any hematologic or metabolic abnormalities. This will require a total of 9 mL of blood to be collected from each subject.

ECG: An ECG will be obtained at baseline and at 30 days to measure each subject's QT interval and monitor for QTc prolongation or other arrhythmias.

Adverse event survey: A questionnaire to screen for adverse events will be administered by study personnel at 7 days by phone interview (Appendix H). This 7-day evaluation will be done in person if the patient has not been discharged from the hospital yet. The same questionnaire will be administered when the subjects return to the University of Rochester Stroke and Cerebrovascular Disorders Clinic for their follow-up visits at 30 and 90 days. Finally, the same questionnaire will be administered at 6 months by phone interview.

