5.7. Return of Individual Research Results

Individual research results will not be routinely made available to study subjects. However, they will have access to many of their test results upon request or through the online patient medical record access system, MyChart. With the exception of the serial fMRI studies, baseline and 60-day OCT studies, the PHQ-9, VFQ-25, and adverse event questionnaires, and the ECG, CBC, CMP, and Humphrey visual field testing performed at 30 days, all proposed evaluations are part of the routine care and work-up of stroke patients with visual field deficits. Results of these evaluations will be included in the medical record. Any incidental findings of potential clinical significance, discovered in the course of a study-specific evaluation that falls outside standard care, will be immediately disclosed to the patient and his or her primary care physician. Follow-up studies or consultations will also be recommended to the primary care physician as appropriate.

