9. SAFETY AND REPORTABLE EVENTS

9.1. Adverse Event Definition

An adverse event is any symptom, sign, illness, or medical experience that develops or worsens during the course of the study, whether it is attributable to the study drug or not.

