9.3. Recording Adverse Events

As specified in the Table, study personnel will screen each subject for adverse events at 7 days, 30 days, 90 days, and 6 months by recording all voluntary complaints of the subject, administering the adverse event questionnaire, and evaluating any available objective clinical findings.

All adverse events, whether observed by study personnel, or elicited from or volunteered by the subject, will be documented. Documentation will include a brief description of the experience, the date of onset, the date of resolution, the duration and type of experience, the severity, any relationship to the study drug, any contributing or alleviating factors, and any action taken with respect to the study drug.

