9.4. Responsibilities for Reporting Serious Adverse Events

The Principal Investigator will record all serious adverse events that occur during the study period in an adverse event log. The study period for reporting serious adverse events will be from the time of signing consent until the final study visit at 6 months (*i.e.* 3 months after stopping the study drug). The Principal Investigator will comply with all RSRB policies and regulations regarding the reporting of adverse events.

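### Stopping drug or emergency unblinding means withdrawal from the study, and the protocol does not say how safety follow-up continues; a voluntary stopper before day 30 has no scheduled post-baseline CBC, CMP or ECG

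*Combined protocol and SAP*

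**What the plan says.** All references are to the combined protocol and SAP.

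**Withdrawal.** Section 8.5 allows a subject to stop study drug at any time and gives the consequence: "Should they do so, they will be withdrawn from the study". Section 8.6 treats emergency unblinding the same way: "Should drug disclosure occur, the subject in question will be withdrawn from the study". Both are mandatory. Section 7 makes withdrawal optional after events such as recurrent stroke, symptomatic hemorrhagic transformation or a serious illness leading to hospital admission. The only next step it names is replacement: "Subjects withdrawn from the study will be replaced".

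**Adverse event recording.** Section 9.1 defines an adverse event as one that "develops or worsens during the course of the study". Section 9.3 says that "study personnel will screen each subject for adverse events at 7 days, 30 days, 90 days, and 6 months", and asks for dates of onset and resolution and for any action taken on the drug. Section 9.4 sets serious event recording "from the time of signing consent until the final study visit at 6 months".

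**Safety tests.** Section 5.3 states: "A CBC and CMP will be repeated 30 days after the initiation of the study drug". It schedules the ECG at baseline and 30 days. The day-7 contact is a questionnaire only. Section 5.7 lists the adverse event questionnaires, "and the ECG, CBC, CMP, and Humphrey visual field testing performed at 30 days", among the items that are not routine care. The schedule Table agrees: it marks the day-30 CBC, CMP and ECG, and every adverse event questionnaire, as study-related.

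**The concern.** A subject who stops capsules because of a suspected side effect is the one in whom sodium, platelets, QTc, mood and the course of the event most need checking. Section 10.1 names hyponatremia, abnormal bleeding, QT prolongation and suicidal behavior among the risks of fluoxetine. Taken literally, Sections 8.5 and 8.6 remove that subject from the schedule that would do the checking. Because the tests and questionnaires are research procedures, the routine clinic visits described in Section 5.5 would not supply them by default.

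At stake are the safety of individual subjects and the completeness of the record that the Principal Investigator reviews monthly under Section 13.3. That review can be no more complete than the events collected.

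**Working it through.** **1. Does a recording duty survive withdrawal?**

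- For: Section 9.3 covers each subject through 6 months. Section 9.4 runs to 6 months, which it explains as three months past the end of dosing, and makes no exception for withdrawn subjects.
- Against: Section 9.1 ties adverse events to the course of the study, which could mean the study period or the individual's participation. Section 9.4 ends at a final study visit, which a withdrawn subject does not have.
- Neither side is settled by Sections 7, 8.5 or 8.6, which describe no early-termination visit, contact route or follow-up of open events.

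So the duty is plausible, but the text does not tell site staff to act on it after withdrawal.

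**2. What does a leaver miss if withdrawal ends scheduled contact?** Four questionnaires are scheduled: 7 days, 30 days, 90 days and 6 months.

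| Time of leaving | Questionnaires still due | Post-baseline CBC, CMP and ECG done? |
|---|---|---|
| Before the day-7 contact | 4 of 4 | No |
| Day 7 to day 30 | 3 of 4 | No |
| Day 30 to day 90 | 2 of 4 | Yes, at day 30 |
| After day 90 | 1 of 4 | Yes, at day 30 |

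Dosing ends at day 90, so the last row can arise only through unblinding or a Section 7 withdrawal, not through stopping drug.

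**3. How many subjects?** Inputs, from Sections 3.1 and 13.1: 40 enrolled, 30 at the end, 25% dropout.

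- The plan's own figure reproduces: 30 / (1 − 0.25) = 40.
- Planned leavers, all causes: 0.25 × 40 = 10.
- The documents do not split these 10 by cause, timing or arm. Those leaving before day 30 could therefore be anywhere from 0 to 10 of 40, and the number who stop because of suspected harm cannot be derived.

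The range holds only at the planned dropout rate. It includes people who fail to return or refuse contact, whom no wording could reach.

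**4. Cost of continued contact.** One call per remaining time point gives 1 to 4 calls per leaver. For 10 leavers that is 10 × 1 = 10 to 10 × 4 = 40 calls.

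**The case against.** The strongest reply is that Sections 9.3 and 9.4 already deal with this. They cover each subject, run to 6 months and exempt no one. They also ask for the action taken on the drug, so the event that leads to stopping should be captured. A phone mode exists too, since Section 5.3 uses it at 7 days and 6 months. Much of this stands. A reader might infer that safety recording ceases at withdrawal, but the documents do not support that. What they lack is a sentence joining the two sets of rules.

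Second, the laboratory gap is narrower than the withdrawal rule. Unblinding under Section 8.6 happens in a medical emergency, and the Section 7 illnesses bring patients under acute care, where tests will be done as needed. This stands, and it leaves the gap mainly with outpatients who simply stop before day 30. For them clinically indicated tests are not barred, but none is scheduled.

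Third, the consent form, the review board policies cited in Section 9.4 and the monitoring guidelines cited in Section 13.3 may add terms. The first two are not in the reviewed text, and Section 13.3 cites the guidelines without stating terms for withdrawn subjects. They may fill the gap, but Sections 8.5 and 8.6 are stated without qualification.

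Fourth, a fixed rule to bring the day-30 tests forward would, for someone who stops after a few doses, nearly repeat baseline and might need an extra visit. This is right, and the fix is limited accordingly.

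**Conclusion.** The point holds as a gap between the withdrawal rules and the safety schedule. Mandatory withdrawal is stated without any follow-up. The continuing duty in Sections 9.3 and 9.4 is arguable but not reconciled with it. A voluntary stopper before day 30 has no scheduled laboratory or ECG check after baseline. An amendment is worthwhile because it is cheap and protects subjects.

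The size is unknown: 0 to 10 of 40 under the planned 25% dropout. A reader might take the dropout rate to mean that a quarter of subjects go unmonitored. The documents do not support that, because the rate covers all causes and all times.

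Nor do they support an inference of bias here. Section 13.2 plans no between-arm safety comparison, and nothing shows which arm would lose more events. What withdrawal does to the 6-month perimetry endpoint is a separate question that this point does not address.

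The conclusion assumes that the unseen consent form and review board policies do not already set out post-withdrawal contact.

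**What to change.** In Sections 7, 8.5 and 8.6, state that stopping drug or being unblinded ends treatment but not safety follow-up. Unless the subject withdraws consent to contact:

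- give the adverse event questionnaire by phone at each remaining scheduled time point to 6 months;
- follow open adverse events to resolution or 6 months, whichever comes first;
- if the subject stops before day 30 because of a suspected drug effect, obtain the already planned CBC, CMP and ECG at or soon after stopping;
- for other early stoppers, leave those tests to the investigator's clinical discretion.

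The cost is amendment wording, the calls counted above and, for a few outpatients, one unscheduled visit for a 9 mL blood draw and an ECG. These tests are in the day-30 plan, but early leavers would not have them if withdrawal ends their scheduled visits, so for those subjects they are in effect added. Some leavers will decline contact.
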